4. RECRUITMENT

Correctional staff member's only role in the recruitment process is to provide the research team with list of the pool of potentially eligible participants at the time of enrollment. As part of this process the correctional staff will use prison records to identify and remove inmates who have an intellectual disability and/or are on restrictions that would preclude him/her from being in group gathering spaces. Members of the research team will conduct all recruitment activities, which includes inviting potentially eligible prisoners to meet with them in a private setting in the prison to learn about the study. During this initial meeting, research staff will provide potential participants with a flyer that described the study and discuss potential participant's questions. In the initial meeting, the research staff emphasize the voluntary nature of the study and that the person's decision about participation has no bearing on their criminal or civil cases.

5. STUDY INTERVENTION

This study will have two study arms: The experimental intervention is T4C-MI and the control condition is Standard Prison Treatment and Programming.

5.a. Experimental Intervention

The research intervention is T4C-MI – Thinking for a Change for prisoners with mental illness. This intervention has two components. The first component is Thinking for a Change (T4C)¹, which is an established, manualized intervention shown to be effective at reducing behavioral infractions and time in administrative segregation among prisoners in the general population. T4C is a highly structured, 25-session, manualized intervention that is delivered in a closed-group format to 8-12 people up to twice a week over 12-14 weeks. The intervention curriculum includes three modules: (1) 10 sessions on social skills training that teach participants cognitive skills to interpret and respond positively to social situations that involve potential conflict; (2) 5 sessions on cognitive restructuring activities that teach participants a concrete process for self-reflection that is designed to help individuals identify and correct maladaptive or dysfunctional thought processes, such as anti-social thoughts, feelings, attitudes and beliefs that could lead to criminal activity; and (3) 10 sessions on problem-solving techniques which integrates the skills from the first two modules into a structured problem-solving method that can be used to manage interpersonally challenging situations. More information on this intervention can be found at in the treatment manual²⁶.

The second component of T4C-MI is the Targeted Service Delivery Approach (TSDA)²⁶ that this research team developed to improve access to interventions like T4C for justice-involved persons with mental illness. The goal of the TSDA is to minimize the impact of neurocognitive and social impairments associated with mental illness on participants' ability to fully engage in and understand T4C's intervention materials. To achieve this goal the TSDA uses five therapeutic strategies during the delivery of T4C. These therapeutic strategies include repetition and frequent summarizing, amplification techniques, active coaching, low-demand practice, and techniques to maximize participation. The therapeutic strategies used in the TSDA are designed to work together during the delivery of the T4C to maximize participants' engagement with the intervention materials during each session. More information on the TSDA can be found in the publication²⁶.

5.b. Control Condition

People assigned to the control condition will receive standard prison treatment and programming. Standard prison treatment and programming includes any mental health services that participants are otherwise eligible to receive from the prison during the study time period. Prison mental health services include a range of treatment services that are designed to help people adjust to incarceration. These services include crisis services focused on addressing suicidal thoughts and behaviors and other mental health crisis; psychiatric evaluation, consultation, and medication management; and individual counseling to help to stabilize a prisoner's mental illness so he or she can function appropriately in the prison environment. Prison staff make all decisions regarding eligibility and allocation of all services and programming offered by the prison.

6. STUDY PROCEDURES

Study participants will complete up to four, face to face interviews. The first interview is the screening interview where study eligibility is determined. Participants who meet the study eligibility criteria are enrolled in the study, randomized into one of the two study conditions. People who are randomly assigned to the experimental condition receive the study intervention and those who are randomly assigned to the control condition receive standard prison treatment and programming. All participants who are randomized to either study condition complete three additional follow up interviews: the baseline interview as well as 3- and 6-month interviews. Additionally, administrative data related to behavioral infractions and administrative segregation are collected at the 9-month time point.

6.a Description of Research Procedures

The study procedures are listed below.

All research interviews will take place in private locations in the prison:

First: Recruitment of study subjects will begin the month prior to the initiation of each intervention cycle. Correctional staff at the facility where the intervention is being delivered, will provide the research team with a list of all of the prisoners in their facility who meet the following criteria: a) 18 years and older: b) have mental health issues: c) have at least 1 year remaining on his or her prison sentence: d) do not have any restriction that would preclude the person from being in group gathering spaces within the prison; and e) do not have an intellectual or developmental disability.

Second: Research staff will go to the prison and invite potentially-eligible prisoners to meet with them in a private setting to learn about the study. During this initial meeting, research staff will provide participants with a flyer that describes the study and discuss potential participant's questions. The study flyer and discussions with potential participants will include information about the voluntary nature of the study and will explain that the person's decision about participation has no bearing on the person's criminal or civil cases. The research staff will also explain that the participant can end his or her participation in the study at any time during the recruitment or study process without negative consequences.

Three: Immediately after completing the recruitment meeting research staff will complete Informed consent with all participants who express interest in participation in the study. This meeting will take place in a private setting in the prison.

Fourth: Research staff will complete a screening interview immediately after the informed consent process with all potential subjects who agree to participate in the study after completing informed consent. The study screening interview will determine whether participants are eligible to participate in the study by screening for mental health diagnoses, criminogenic risk levels, and prior engagement in T4C.

Fifth: At the end of the screening interview potential participants will be informed whether they meet the study eligibility criteria. Participants who are found eligible for the study and agree to participate will be assigned to a study condition. During the RCT phase of the study, participants will be randomized into one of two conditions, the research intervention (T4C-MI) or the control condition (Standard prison treatment and programming). The research staff will randomly assign participants to a study condition by opening a sequentially numbered envelope and discussing the condition assignment with the participant. In order to be sure that interviews are not too long, the screening and baseline interviews will be broken into two separate interviews, conducted at least one day apart from each other. After randomization is complete the research staff will schedule a mutually agreed upon time to return to complete the baseline interview.

Six: Research staff will complete a baseline interview with all study participants. This interview will take place in a private location in the prison. The baseline interview will include a brief assessment of participant's neurocognitive functioning, clinical and criminal justice history, and baseline assessments of treatment targets and study outcomes. The baseline interview will take 60-90 minutes to complete.

Seven: Research staff will complete follow-up interviews with all study participants at 3-, 6 -months after the baseline interview. Each interview is expected to take 30-60 minutes to complete and will be conducted in a private setting in the prison. Participants' outcomes will also be assessed at 9 months post release using administrative data.

6.b Informed Consent

Research staff will engage written Informed consent with all potential participants who express an interest in participation in the study during recruitment. Participants will also be asked to sign a HIPPA Authorization form allowing the study team to collect administrative pertaining to the study outcomes. Given concerns about the heightened risk of coercion that exists when conducting research in correctional settings, the research team took the following steps to minimize the risk of coercion in this study and obtain informed consent. First, although the recruitment process involved correctional staff, the involvement of these staff members was limited to helping the research team identify the pool of potential participants. Second, only the members of the research team approached potential participants to discuss

the study and obtain informed consent. Third, research staff conducted all informed consent meetings, and these meetings were held in private spaces. Fourth, correctional staff were instructed that study participation is strictly voluntary. Fifth, research staff did not communicate the outcomes of potential participant contacts with correctional staff. Taken together, these steps minimized the chance that correctional staff directly or inadvertently tried to influence individuals' decision to participate in the study. All researchers involved in recruitment were trained to cover consent information clearly and comprehensively. Furthermore, study flyers, consent forms, and HIPAA authorization forms were made available, in print form, to all potential participants.

6.c. Assessments and Data Collection

All study measures, with the exception of the receipt of Behavioral Infractions and Time Spent in Administrative Segregation, will be administered in face-to-face interviews using a paper-based interview. Receipt of Behavioral Infractions and Time Spent in Administrative Segregation are collected via administrative data. See appendix A for descriptions of study measures.

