Study Phases	
(1) Study Recruitment and Informed Consent
 
A) Prison Staff will provide study personnel with list of potentially eligible participants.B) Study staff will invite potentially eligible participants to meet with them to discuss study. Study staff will complete informed consent with all potential participants who agree. 
(2) Study Screening- All potential participants who agree to participate in the study after informed consent is completed will participate in a screening interview to determine study eligibility.
 
(3) All participants who are found eligible at the end of the screening interviews will be randomized to one of the two study arms (e.g. experimental or control condition). These individuals will make up the study sample
 
(4) Baseline interviews will be completed with all study participants.
 
(5) Study participants who are randomized into the experimental condition will participate in the study intervention. Those who are randomized into the control condition will receive standard prison treatment and programming.
 
(6) Follow up: Study participants will participate in follow-up interviews at 3- and 6- months post-baseline.
 
(7) Administrative data related to behavioral infractions and administrative segregation will be gathered at 9-months post-baseline.

Screening	
Study Treatment	
Follow-Up	

The statistical analyses of this study will explore the treatment effect of the study intervention on the study outcomes (aggression, receipt of behavioral infractions, and time spent in administrative segregation) and the study treatment targets (impulsivity, social problem solving, and criminal attitudes and associates). Additionally, mediation analyses will be conducted to explore whether treatment effects on study outcomes operate indirectly through study treatment targets.

DATA AND SAFETY MONITORING PLAN	This is a small-scale, pilot study with a relatively small number of subjects; thus, in lieu of a Data and Safety Monitoring Board, the PI will perform the monitoring function as part of the general oversight and scientific leadership of the study
---------------------------------	---

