3. STUDY DESIGN

This study will engage a pilot effectiveness trial to examine the extent to which T4C-MI impacts its intended targets (mediating mechanisms) and outcomes among prisoners with SMI. The study will use a randomized controlled design to assign participants to one of the two study arms 1) the study intervention (T4C-MI) or 2) Standard Prison Treatment and programming. The study will take place in the North Carolina Prison system and will involve up to four facilities.

3.a. Allocation to Treatment Groups

In this study randomization will take place on site at the prison, which does not allow electronic equipment to be brought into facilities. Therefore, the study team will use a shuffled envelope to randomize participants on site at the prison. The study team will use a table of computer-generated random numbers and block randomization procedures to ensure an equal distribution of subjects to each arm of the study. Study staff will not be blinded to participant condition.

3.b. Study Duration, Enrollment and Number of Subjects

The study will be active for 4 years. Each participant will be involved for 9 months.

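### The baseline for aggression and the three treatment targets is taken at least a day after participants learn their arm; moving the envelope to the end of the baseline visit corrects this cheaply, but not assignment-aware reporting at follow-up

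*Combined protocol and SAP*

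**What the plan says.** Every part of the document that describes the sequence gives the same order.

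- **Synopsis, Study Phases.** Step 3: "All participants who are found eligible at the end of the screening interviews will be randomized to one of the two study arms". The baseline interview is step 4.
- **Section 6, opening paragraph.** Randomized participants "complete three additional follow up interviews: the baseline interview as well as 3- and 6-month interviews", so baseline is listed among the interviews that come after allocation.
- **Section 6.a, Fifth.** Staff assign the condition by "opening a sequentially numbered envelope and discussing the condition assignment with the participant". The screening and baseline interviews "will be broken into two separate interviews, conducted at least one day apart from each other"; the only reason given is interview length. Then: "After randomization is complete the research staff will schedule a mutually agreed upon time to return to complete the baseline interview".
- **Section 6.a, Fourth and Six.** Screening covers diagnosis, criminogenic risk and earlier T4C participation. The first assessment of outcomes and treatment targets belongs to the baseline interview.
- **Appendix A.** Randomization is in the screening column. The four scales first appear in the baseline column.

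On measurement conditions, section 3.a says "Study staff will not be blinded to participant condition", and section 6.c says that all measures except the two administrative outcomes "will be administered in face-to-face interviews using a paper-based interview".

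Section 9.c plans posttest t-tests and mixed linear models for the four scales. Section 9.d counts on each participant acting as his or her own control to gain power.

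**The concern.** A baseline should be free of any influence from allocation. Here participants know whether they will be offered T4C-MI, and so does the interviewer, when the AQ-Short, SPSI-R:L, MCAA and BIS-11 are first completed. A difference between arms at that interview could be chance or a reaction to the assignment, and no earlier value of these scales exists to tell which.

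Three things are at stake.

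1. **Estimates that use baseline.** If knowing the arm shifts baseline answers by some amount, change and posttest estimates of the same scale differ in expectation by that amount. The data cannot show which is nearer the truth. Appendix A schedules two occasions for the treatment targets and three for aggression, so this interview is half or a third of the planned data on these scales.
2. **Loss between allocation and baseline.** Section 11.b allows withdrawal on request and removal on transfer or release. Anyone lost in the gap is randomized with no baseline value, possibly unevenly by arm. A mixed model can still use that person's follow-up data, if there are any.
3. **Planning the later trial.** Section 9.d gives this as a main purpose. Means and changes referred to this baseline would carry the ambiguity forward.

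The scope is one of three primary outcomes (aggression) and the three secondary outcomes. Infractions and segregation have no baseline, and the posttest t-tests do not use it.

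**Working it through.** The order of steps needs no arithmetic; the passages agree. The plan has no figure to reproduce on this point: 112 is a ceiling, with no alpha, SD or effect size behind it. The calculation below only shows what could follow.

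**Inputs.** From the documents: up to 112 participants, allocated equally, so at most 112/2 = 56 per arm. Assumed: two-sided 5% test, SD 1, no true effect, baseline reporting shift d = 0.2 SD, correlation between baseline and follow-up ρ = 0.6, and share p of the shift still present at follow-up. Section 9.c states no time coding, group-by-time term or baseline adjustment, so two simple contrasts (change score and baseline-adjusted) stand in for the mixed model.

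**Bias.**

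| Estimate | Present order | Envelope after baseline |
|---|---|---|
| Posttest | d·p | d·p |
| Change | d(p − 1) | d·p |
| Baseline-adjusted | d(p − ρ) | d·p |

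**Standard errors at n = 56 per arm.**

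- Posttest: √(2/n) = √(2/56) = 0.189
- Change: √(4(1 − ρ)/n) = √(1.6/56) = 0.169
- Adjusted: √(2(1 − ρ²)/n) = √(1.28/56) = 0.151

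**Rejection rate** = P(|Z + bias/SE| > 1.96). For example, change with p = 0 in the present order: bias −0.20, ratio −0.20/0.169 = −1.18, rate 21.9%.

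False rejection, present order → envelope after baseline:

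| p | Change | Adjusted | Posttest (both orders) |
|---|---|---|---|
| 0 | 21.9% → 5.0% | 12.5% → 5.0% | 5.0% |
| 0.25 | 14.4% → 6.0% | 7.5% → 6.3% | 5.8% |
| 0.5 | 9.1% → 9.1% | 5.2% → 10.1% | 8.3% |
| 0.75 | 6.0% → 14.4% | 5.5% → 16.8% | 12.5% |
| 1 | 5.0% → 21.9% | 8.3% → 26.3% | 18.5% |

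A simulation with t-tests and ANCOVA (20,000 trials per cell, at p = 0, 0.5 and 1) agreed to within about half a percentage point.

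**Break-even.** The new order has the smaller absolute bias when p < 1 − p, that is p < 0.5, for change, and when p < ρ − p, that is p < ρ/2, for the adjusted contrast (0.2, 0.3 and 0.4 at ρ = 0.4, 0.6 and 0.8). Above those points it has the larger bias.

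**Range over d = 0.1 to 0.3 and ρ = 0.4 to 0.8, n = 56.**

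| p | Change | Adjusted |
|---|---|---|
| 0 | 7.7–70.9% → 5.0% | 5.6–56.2% → 5.0% |
| 0.5 | 5.7–24.1% in both orders | 5.0–12.5% → 6.0–26.3% |
| 1 | 5.0% → 7.7–70.9% | 5.4–18.0% → 8.9–75.4% |

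With 40 per arm (d = 0.2, ρ = 0.6), p = 0 gives 17.0% (change) and 10.3% (adjusted) → 5.0% for both; p = 1 gives 5.0% → 17.0% and 7.3% → 20.1%.

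**Would a baseline comparison reveal it?** Rarely. The standard error of the difference between arms is 0.189 SD, so a true 0.2 SD shift (0.2/0.189 = 1.06) reaches p < 0.05 only 18.5% of the time.

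**What is not harmed.** A constant shift within an arm leaves within-arm SDs and pre-post correlations alone. In the simulation the within-arm correlation stayed at 0.597–0.599 for an input of 0.6. Those planning quantities survive.

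**The case against.** The strongest objection is that the table shows no general gain in error rate. The arm is known and staff are unblinded at follow-up just as at baseline, so a persisting shift is at least as credible as one that fades. With p = 1 the present order does better on both contrasts. Nor need p lie between 0 and 1: by month 3 the experimental arm has been offered 25 sessions, so the shift could grow or reverse. At p = 1.5 the move takes change from 9.1% to 42.7% and adjusted from 22.2% to 51.0%. At p = −0.5 it takes them from 42.7% to 9.1% and from 30.7% to 10.1%. This stands: the move cannot be sold as always lowering bias. It does not rescue the present order, whose cancellation is accidental, of unknown size, and different for each contrast. The break-even rules also hold outside 0 to 1.

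The contrasts modelled are not the planned mixed model. This too stands. For aggression, averaging both follow-ups (compound symmetry, ρ = 0.6) gives a change SE of √(2 × 0.6/56) = 0.146 and a rate of 27.7% at p = 0, rather than 21.9%. The percentages illustrate; they are not predictions.

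The consequence is limited. Two of three primary outcomes are untouched, section 9 calls the analyses inconclusive, and section 9.d disclaims effect-size estimation. That keeps the point from being a blocking one.

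Finally, section 6.b describes consent meetings in the past tense, so enrollment may be over. In that case only the reporting step below remains.

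**Conclusion.** The concern holds. The synopsis, section 6, section 6.a and Appendix A all place disclosure of the arm before the first measurement of aggression and the three treatment targets, and nothing in the plan compensates. Confidence is high for the order of steps only. The size, direction and persistence of any shift are unknown, and every percentage above rests on assumed values.

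The case for change does not depend on a favourable value of p. With the envelope opened after baseline, posttest, change and adjusted estimates share one expectation. One limitation is then left to declare, reporting influenced by known assignment at months 3 and 6, in place of an unknown disagreement between estimates. No one is lost between allocation and baseline. For a pilot that disclaims conclusive testing this should be fixed because it costs little; it is not a reason to stop.

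**What to change.** **If enrollment is still open.** Keep both visits. Tell participants at screening whether they are eligible, complete the baseline interview at the second visit, and only then open the next sequentially numbered envelope. Amend the synopsis (Study Phases), section 6, section 6.a and Appendix A together. Continue to count eligible people who do not reach baseline, since attrition and retention are a stated purpose in section 9.d. State as a limitation that participants and interviewers still know the arm at months 3 and 6, and do not claim that the new order always reduces bias.

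**For anyone already randomized before baseline.** Add one sentence to section 9.c: report posttest and baseline-referenced estimates side by side, with baseline means by arm and the number lost between allocation and baseline, and give neither the lead on grounds of bias. A posttest comparison adjusted for variables collected at screening before the envelope (Level of Service Inventory, background characteristics) could be added; these are only proxies for the four scales.

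**Cost.** Protocol wording only, with no extra visit, interview or staff. The one drawback is that the roster for each closed group is known later, by the gap between visits: at least one day, with no upper limit stated. Baselines must therefore be finished before the group starts. Section 6.a leaves some room for this: "Recruitment of study subjects will begin the month prior to the initiation of each intervention cycle".
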